# 11.1.1 Serious Adverse Event Reporting on Study Post-Unblinding

Serious adverse events that are considered related (i.e. possibly, probably or definitely) to protocol therapy must continue to be reported in an expedited manner (see section 11.2) for patients receiving BBI608 on study after unblinding.

### 11.2 Serious Adverse Event Reporting Instructions

All protocol specified (section 11.1) reportable serious adverse events must be reported using the web-based Electronic Data Capture (EDC) system being used for this trial. For details about accessing the EDC system and completing the on-line SAE report form, please refer to the NCIC CTG Generic Data Management Guidebook for EDC Studies posted on the CO.23 section of the NCIC CTG website (www.ctg.queensu.ca).

Within 24 hours: Complete preliminary Serious Adverse Event Report and submit to

NCIC CTG via EDC system.

Within 7 days: Update Serious Adverse Event Report as much as possible and

submit report to NCIC CTG via EDC system.

### *EDC SAE web application interruption:*

In the rare event that internet connectivity to the EDC SAE system is disrupted, please print and complete a paper copy of the SAE Report, available from the trial specific website.

FAX paper SAE Report to: CO.23 Study Coordinator

NCIC Clinical Trials Group [contact]

Please use the same timelines for submission as for direct EDC reporting.

Once internet connectivity is restored, the information that was FAXED to NCIC CTG on the paper SAE Report must also be entered by the site into the EDC SAE web application.

#### *Local internet interruption:*

If you are unable to access the EDC SAE system, and cannot access a paper copy of the SAE Report from the trial website, please phone the CO.23 trial team [contact]) to obtain a copy of the SAE Report by FAX. Once completed, the report must be FAXED back to NCIC CTG as indicated above. Once internet connectivity is restored, the information that was FAXED to NCIC CTG on the paper SAE Report must also be entered by the site into the EDC SAE web application.

In cases of prolonged internet interruptions, please contact the NCIC CTG Safety Desk for further instructions [contact]).

# 11.3 Other Protocol Reportable Events – Pregnancy/Exposure Reporting

In accordance with NCIC CTG's inclusivity in research policy, women of childbearing potential (WOCBP) may be enrolled in this clinical trial. WOCBP are defined as women who have had a menstrual period during the last year and have not had a hysterectomy. Precautions are required to be taken to prevent pregnancy during the clinical trial when the research population includes WOCBP. This includes pregnancy testing, use of effective methods of birth control, and pregnancy as an exclusion factor. The trial sample informed consent form includes *the potential for unidentified risks to the embryo/fetus*. It also includes general information on pregnancy prevention and the required minimum period during which birth control must be utilized.

#### 11.3.1 Pregnancy Prevention

WOCBP and males who are enrolled in the trial must be informed of the requirement to use contraception as outlined in eligibility criteria 5.1.12. Investigators are advised to inform the female partners of male participants when appropriate and compliant with local policy.

A highly effective method of birth control is defined as those which result in a failure rate of <1% per year when used consistently and correctly.

# 11.3.2 Pregnancy Occurring in WOCBP Exposed to Study Agent

Any female participant who becomes pregnant during the course of the trial should be instructed to stop taking study medication immediately.

The investigator should provide counselling and discuss the risks and possible side effects to the embryo/fetus from BBI608. Monitoring should continue until conclusion of the pregnancy. The same should occur for female partners of a male participant, or any female exposed to BBI608 when appropriate and compliant with local policy.

# 11.3.3 Pregnancy/Exposure Reporting

The investigator is required to report to the sponsor any pregnancy where the embryo/fetus could have been exposed to BBI608. This means pregnancies occurring in female participants, female partners of male participants, or females exposed through direct contact with the agent during their pregnancy (for example, environmental exposure involving direct contact with the agent). Pregnancies occurring up to 30 days after the completion of BBI608 must also be reported.

The investigator is required to inform NCIC CTG within 24 hours of learning of the pregnancy using the SAE reporting form appropriate for the trial as indicated above. In the Adverse Event column please enter the following: "pregnancy, puerperium and perinatal conditions – other, specify" (fetal exposure). Please note that the NCIC CTG patient identification number must correspond to the participant in the main trial. Specifically, in the case of pregnancy in the female partner of a male participant, the male participant's patient identification number should be used for reporting purposes.

The SAE form must be updated to reflect the outcome of the pregnancy. For example:

- "pregnancy, puerperium and perinatal conditions other, specify" (normal live birth),
- "pregnancy, puerperium and perinatal conditions other, specify" (therapeutic abortion), or
- another term under "pregnancy, puerperium and perinatal conditions" as applicable.

Information on the medical history of the parents that may relate to assessing any potential fetal outcomes is requested, *as is information on the health of the newborn*. The narrative section of the SAE form should be used to communicate all relevant information pertaining to the pregnancy.

# 11.4 NCIC CTG Responsibility for Reporting Serious Adverse Events to Regulatory Agencies

The NCIC CTG will provide expedited reports of SAEs to Health Canada (Office of Clinical Trials) and local country sponsors (for submission to applicable regulatory authorities), for those events which meet regulatory requirements for expedited reporting, i.e. events which are BOTH serious AND unexpected, AND which are related to protocol treatment:

- Unexpected adverse events are those which are not consistent in either nature or severity with information contained in the Investigator's Brochure
- Adverse events considered **related to protocol treatment** are those events which lack a plausible alternate explanation.

NCIC CTG, in consultation with Boston Biomedical Inc, will determine which SAEs meet the criteria for regulatory reporting.

# 11.5 NCIC CTG Reporting Responsibility to Boston Biomedical, Inc.

Boston Biomedical, Inc will be notified of all serious adverse events within 1 working day of receipt by NCIC CTG. Boston Biomedical will have electronic access to Serious Adverse Event information for the purposes of assisting the NCIC CTG as requested in determining which SAEs meet the criteria for regulatory reporting.

## 11.6 Boston Biomedical, Inc Reporting Responsibilities

Boston Biomedical will notify the NCIC CTG of all Safety Letters/Safety Updates (SUs) or Serious Adverse Events (SAEs) that are reported to regulatory authorities from other trials involving BBI608.

# 11.7 Reporting Safety Reports to Investigators

NCIC CTG will notify Investigators of all Safety Reports (Serious Adverse Events (SAEs) from this trial and Safety Updates (SUs) from other clinical trials) that are reportable to regulatory authorities in Canada as reported to the NCIC CTG. This includes all serious events that are unexpected and related (i.e. possibly, probably, or definitely) to protocol treatment. The reports will be posted to the NCIC CTG trial CO.23 web-based safety monitoring utility.

Investigators must notify their Research Ethics Boards (REBs) of events which involve corrective action(s) to be taken as a result of the event(s) such as protocol and/or informed consent changes. The date of REB Submission for these SAEs and SUs will need to be entered into the NCIC CTG trial CO.23 web based safety monitoring utility and documentation of REB submission must be retained in the study binder on site. The REB submission template provided by NCIC CTG can be used to assist with tracking, submission, filing and monitoring.

The submission of events to your ethics board should be done as soon as possible (we suggest within 30 days). REB submissions greater than 90 days from the date of notification will be regarded as delinquent and a major deficiency will be assigned. These safety reports are to be filed in the trial files on site.

AMEND #3: 2014-OCT-01

## 12.0 PROTOCOL TREATMENT DISCONTINUATION AND THERAPY AFTER STOPPING

# 12.1 Criteria for Discontinuing Protocol Treatment

Patients should stop protocol treatment in the following instances:

- Progressive Disease (see section 10.2.5), unless the Investigator believes the patient may be deriving benefit from therapy, in which case patient may continue treatment (see section 12.2).
- Pregnancy.
- Intercurrent illness which would, in the judgement of the investigator, affect assessments of clinical status to a significant degree, and require discontinuation of protocol therapy.
- Unacceptable toxicity as defined in section 8.1.5 and 8.1.6.
- Request by the patient.
- Post-unblinding, the trial will continue in centres with patients who have not yet met the primary study endpoint (death), and with patients currently on protocol therapy (active arm) who may receive BBI608 on study based on the clinical judgement of the investigator and local REB approval that this is in the patient's best interest, providing the patient is fully informed and provides consent (see also section 9.1.1 and 9.2.1). Patients will receive study supply BBI608 until any of the discontinuation criteria are met (as above).

Efforts should be made to maintain the investigations schedule and continue follow-up, even if patients discontinue protocol treatment prematurely and/or no longer attend the participating institution. In particular, for patients who discontinue protocol therapy prior to their first objective assessment of response, it is imperative that an objective response assessment be undertaken as close to the protocol specified schedule as possible in order to ensure patient data contributes to the interim assessment of DCR (see section 14.5).

#### 12.2 Duration of Protocol Treatment

Patients may continue to receive protocol therapy as long as they have not experienced any adverse events requiring permanent discontinuation of study medication and are, in the opinion of the investigator, continuing to derive benefit from protocol treatment.

As BBI608 targets cancer stem cells, it is possible that continued therapy after progressive disease per RECIST 1.1 may provide clinical benefit. Therefore, subjects will be permitted to remain on BBI608/placebo beyond formal objective progression until the Investigator believes the patient is no longer deriving benefit from protocol therapy. Thus, subjects may remain on BBI608/placebo beyond formal objective progression by RECIST 1.1 during, or as a component of, palliative care.

# 12.3 Therapy After Protocol Treatment is Stopped

Treatment after all protocol therapy has been discontinued is at the discretion of the Investigator.

# 12.4 Follow-up Off Protocol Treatment

Follow-up will continue after treatment completion according to the plan described in the protocol (see section 9.2). Efforts should be made to maintain the investigations schedule and continue follow-up, even if patients discontinue protocol treatment prematurely and/or no longer attend the participating institution.

# 12.5 Emergency Unblinding

Details of the circumstances in which emergency unblinding is permitted and process to unblind patient treatment are contained in Appendix IX.

# 13.0 CENTRAL REVIEW PROCEDURES, TISSUE COLLECTION, AND CORRELATIVE STUDIES

# 13.1 Central Radiology Review

There will be no central radiology review for this study.

# 13.2 Central Pathology Review

There will be no central pathology review for this study.

# 13.3 Tissue Collection

#### Protocol-Mandated Correlative Studies:

The submission of a representative block of the diagnostic tumour tissue (at the request of the NCIC CTG Central Tumour Bank if available) and of a sample of whole blood for correlative studies defined in Appendix VI is mandatory for participation in this trial. Where local centre regulations prohibit submission of blocks of tumour tissue, the approval of the NCIC CTG must be sought prior to randomization of the first patient to allow cores (two 2 mm cores of tumour from the block) and a predetermined number of slides of representative tumour tissue to be substituted in response to the Central Tumour Bank request. Failure to submit any tissue samples as directed (blood) or on request (tumour tissue) will result in the patient being considered ineligible. Where no previously resected or biopsied tumour tissue exists, on the approval of the NCIC CTG, the patient may still be considered eligible for the study.

The subsequent banking of collected diagnostic tissue or blood is not mandatory for participation in the study, but the participation of all centres is strongly encouraged. Blocks and blood will be carefully banked as part of the NCIC CTG tissue/tumour bank at Queen's University in Kingston, Ontario.

After patient consent, whole blood and paraffin tumour blocks will be the preferred tissue material to collect, as one of the objectives will be to create tissue micro arrays. These will optimize the amount of tissue available to investigators and permit the preservation of the tumour block submitted. If tumour blocks are unavailable, then two 2 mm cores of tumour from the block and 30 specimen slides are preferred. If, at any time, the submitting hospital requires the block to be returned for medical or legal concerns, it will be returned by courier on request.

The tissue may be used by researchers now or in the future to better understand the nature of colorectal cancer and how patients respond to treatment. Samples will be used for research purposes only and will not be sold. A scientific review process of any proposals to use the tissue will take place and any proposals approved will have undergone ethics approval. Patients will not be identified by name. The only identification of tissue will be by a patient study number assigned at the time of randomization to the trial the surgical/ histology number and/or patient initials. Material issued to researchers will be anonymous and only identified by a coded number.

Diagnostic pathology reports are received as part of the supporting documentation required for this trial. Receipt of these will initiate a request directly from the Queen's Department of Pathology to the appropriate pathology departments for a representative tumour block.

Testing for hereditary genetic defects predisposing to malignant disease will not be carried out without the expressed consent of the patient.

All patients on whom a blood sample and/or diagnostic tumour block is collected will be aware of this retrieval and will have given their consent.

# 13.4 Sparse Pharmacokinetic Plasma Sample Collection

Plasma samples for sparse pharmacokinetics (PK) analysis will be obtained from all patients at the study visits occurring 4, 8 and 12 weeks after randomization.

#### Week 4 Study Visit:

The week 4 visit should be scheduled prior to 10 AM. On the day of the week 4 visit, patients should be instructed to wait to take their first daily dose of BBI608/Placebo until they arrive in clinic. After arrival in the clinic, but 5 minutes prior to administration of the first daily dose of BBI608/Placebo, a plasma sample will be obtained. A second plasma sample will be obtained between 2 and 4 hours after the first daily dose of BBI608/Placebo.

# Week 8 Study Visit:

On the day of the week 8 visit, patients will be instructed to take BBI608/Placebo as normal. A single plasma sample will be obtained between 5 and 10 hours after the first daily dose of BBI608/Placebo.

#### Week 12 Study Visit:

On the day of the week 12 visit, patients will be instructed to take BBI608/Placebo as normal. A single plasma sample will be obtained at any time after the first daily dose of BBI608/Placebo on this day.

For all days during which a plasma sample is obtained for PK analysis, the precise time of all doses of BBI608/Placebo (on the day of sampling and the day prior) and the precise time of all PK sampling must be captured.

Samples will be processed, stored and shipped according to the instructions provided in the CO.23 Sparse PK sampling laboratory manual.

## 14.0 STATISTICAL CONSIDERATIONS

# 14.1 Objectives and Design

The primary objective of this study is to assess the effect of orally administered BBI608 plus best supportive care (BSC), in comparison to placebo plus best supportive care on the Overall Survival of patients with advanced histopathologically confirmed colorectal carcinoma who have exhausted all standard treatment options.

Secondary objectives include comparisons of Progression Free Survival, Disease Control Rate, Quality of Life, and Adverse Events between the two treatment arms.

This is a multi-centre, prospective, double blind, placebo controlled, randomized phase III trial. Patients will be randomized to receive either BBI608 plus best supportive care, or placebo plus best supportive care in a 1:1 ratio and will be stratified by ECOG performance status (0 *versus* 1), *K-ras* tumour status (wild type *versus* mutant), prior anti-VEGF therapy (yes *versus* no), and time from diagnosis of metastatic disease to randomization (< 18 months *versus*  $\ge$  18 months).

# 14.2 Study Endpoints and Analysis

# Overall Survival

Overall Survival, the primary endpoint of this study, is defined as the time from randomization to death from any cause. Patients who are alive at the time of the final analysis or who have become lost to follow-up will be censored at their last date known to be alive. Patients will be analyzed in the arm to which they are randomized regardless of the treatment they received (intent-to-treat analysis). The survival experience of patients in both treatment groups will be summarized by the Kaplan-Meier method and compared primarily by a stratified log-rank test adjusting for stratification variables, at randomization. Secondary analyses based on stratified Cox proportional hazards model will also be performed. ECOG performance status (0 versus 1), K-ras tumour status (wild type versus mutant), prior anti-VEGF therapy (yes versus no), and time from diagnosis of metastatic disease to randomization (< 18 months  $versus \ge 18$  months) will be the stratification factors to define the stratified Cox proportional hazards model. Besides the treatment factor (BBI608+BSC versus placebo+BSC), the following factors at patient entry will be included in the stratified Cox proportional hazards model:

- Number of previous chemotherapy drug classes [irinotecan, oxaliplatin, anti-thymidylate synthase drug, EGFR inhibitor, VEGF inhibitor], including during adjuvant therapy (< 3 versus ≥ 3)
- Age  $(< 65 \ versus > 65)$
- Sex (male *versus* female)
- Number of organ sites involved at baseline ( $\leq 2 \ versus > 2$ )
- Presence of liver metastases (yes *versus* no)
- Primary tumour site (colon *versus* rectum)

A formal pre-planned subset analysis for the primary endpoint (OS) will be conducted to address the benefit of BBI608 between the groups defined by the above factors and the following:

- ECOG Performance Status (0 versus 1)
- K-ras (wild type versus mutant)
- Prior bevacizumab exposure (prior treatment versus treatment naïve)
- Prior anti-VEGF (e.g. bevacizumab, aflibercept, etc) therapy (yes *versus* no)
- Time from diagnosis of metastatic disease to randomization (< 18 months versus > 18 months)
- Race (white, black, Asian, other)
- Country (Canada, Australasia, USA, others)

## **Progression-Free Survival**

Progression-Free Survival (PFS) is defined as the time from randomization to the first objective documentation of disease progression or death due to any cause. If a patient has not progressed or died at the time of final analysis, PFS will be censored on the date of the last tumour assessment. This includes patients who are lost to follow-up or have withdrawn consent. All analyses for OS will also be performed for PFS, using similar methodology.

## Disease Control Rate

Disease Control Rate (DCR) is defined as the proportion of patients with a documented complete response, partial response, and stable disease (CR + PR + SD) based on RECIST 1.1. The primary estimate of DCR will be based on all patients randomized.

## Safety Analysis

All patients who have received at least one dose of BBI608/Placebo will be included in the safety analysis. The incidence of adverse events will be summarized by type of adverse event and severity using the NCI Common Terminology Criteria for Adverse Events Version 4.0. A Fisher's exact test will be used to compare adverse events between the two arms if required.

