# 9.1 Evaluation During Protocol Treatment

	Investigations	Timing from Randomization	
Physical Examination	
 
Physical examination
 
Vital signs
 
Weight + ECOG Performance status
 
		
Hematology  • CBC + differential, Platelet count  • Creatinine, Total Bilirubin, ALT, Alkaline Phosphatase, LDH, Albumin, Potassium, Magnesium, Phosphate  • CBC + differential, Platelet count			
		Every 4 weeks (every 28 days) after	
Urinalysis	Dipstick (including protein, specific gravity, glucose and blood)	randomization 	
Economics	Resource Utilization Assessment		
Other Investigations	• Serum or urine pregnancy test 		
Other Investigations	Serum CEA		
	• Adverse Event evaluation must be done at each study visit for the preceding 4 week reporting period 		
Adverse Events 	• Adverse Event evaluation by phone to assess tolerability of dosing regimen 	Within 24-48 hrs of start of protocol treatment, and at 2 weeks (approximately 14 days) and 6 weeks (approximately 42 days) after randomization	
Cardiology Assessment	• ECG	2 hours after first dose on first day of treatment and as clinically indicated thereafter	
Radiology & Imaging	CT/MRI scan as per baseline assessment with tumour measurement and evaluation by RECIST 1.1 criteria 	Every 8 weeks (every 56 days) after randomization 	
Correlative Studies & Tissue Banking	
 
Submission of whole blood sample to central tumour bank 
 
	At 4, 8 and 12 weeks after randomization 	
Sparse PK Collection	• Submission of blood plasma samples to central lab 	At 4, 8 and 12 weeks after randomization 	
Quality of Life	• EORTC QLQ-C30 	At 4, 8, 12, 16 and 24 weeks after	
Health Utilities	• Health Utilities Index (HUI3) 6	randomization	

 Patients are to be assessed every 4 weeks (28 days) while on study medication and until the first regularly scheduled 4 week assessment at which the patient has been off study therapy for a minimum of 28 days.

In women of childbearing potential only a negative pregnancy test must be demonstrated every 4 weeks until 4 weeks after the administration of the final dose of protocol therapy. The minimum sensitivity of the pregnancy test must be 25 IU/L or equivalent units of HCG.

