#### 9.2 Evaluation After Protocol Treatment Discontinuation

Investigations		Timing from Randomization	
Physical Examination	
 
Physical examination
 
Vital signs
 
Weight + ECOG Performance status
 
	Every 4 weeks (every 28 days) after randomization until the first regularly scheduled 4 week	
Economics	Resource Utilization Assessment	assessment at which the patient has been off study therapy for a minimum of 28 days, and every 8	
Adverse Events 	* Adverse Event evaluation must be done at each study visit for the preceding reporting period 	weeks (56 days) thereafter until deterioration to ECOG PS 4 or hospitalization for end of life care.	
Overall Survival	• Assess for survival of patient 	Every 4 weeks (every 28 days) after randomization until the first regularly scheduled 4 week assessment at which the patient has been off study therapy for a minimum of 28 days, and every 8 weeks (56 days) thereafter.	
Other	• Serum or urine pregnancy test 		
Investigations	Serum CEA		
Hematology	CBC + differential, Platelet count	Every 4 weeks (every 28 days) after randomization	
Biochemistry	Creatinine, Total Bilirubin, ALT,     Alkaline Phosphatase, LDH, Albumin,     Potassium, Magnesium, Phosphate	until the first regularly scheduled 4 week assessment at which the patient has been off stud therapy for a minimum of 28 days	
Urinalysis	Dipstick (including protein, specific gravity, glucose and blood)		
Cardiology Assessment	• ECG	At the first regularly scheduled 4 week assessment at which the patient has been off study therapy for a minimum of 28 days	
Radiology & Imaging	• CT/MRI scan as per baseline assessment with tumour measurement and evaluation by RECIST 1.1 criteria 	Every 8 weeks (56 days) after randomization until objective disease progression is documented 	
Correlative Studies & Tissue Banking	• Submission of whole blood sample to central tumour bank 	At 4, 8 and 12 weeks after randomization 	
Quality of Life	• EORTC QLQ-C30 	At 4, 8, 12, 16 and 24 weeks after randomization or	
Health Utilities	• Health Utilities Index (HUI3) 6	until deterioration to ECOG PS 4 or hospitalization for end of life care 	

 Adverse events will be recorded and graded according to the NCI Common Terminology Criteria for Adverse Events (see Appendix V).

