## 11.1 Definition of a Protocol Reportable Serious Adverse Event

- All serious adverse events must be reported in an expedited manner (see section 11.2 for reporting instructions). These include events occurring during the treatment period (until 30 days after last protocol treatment administration).
- A serious adverse event (SAE) is any adverse event that at any dose:
  - results in death;
  - is life-threatening;
  - requires inpatient hospitalization or prolongation of existing hospitalization (excluding hospital admissions for study drug administration, transfusional support, scheduled elective surgery and admissions for palliative or terminal care);
  - results in persistent or significant disability or incapacity;
  - is a congenital anomaly/birth defect.
- NOTE: Serious adverse events which are unequivocally related to the underlying malignancy or disease progression do NOT require expedited reporting. These include such adverse events as admission for pain control, palliative care or paracentesis of malignant effusions.
- In addition, the following events will **NOT** be recorded as AEs (or SAEs):
  - lack of efficacy /disease progression (will be recorded separately on CRF);
  - laboratory abnormalities for protocol specified tests (these are derived electronically from actual values supplied and need not be reported separately in adverse event tables on CRFs);
  - elective hospitalization for medical, radiological or surgical procedures for treatment of disease or to simplify treatment for study procedures (will be recorded separately on CRF):
  - hospitalization for palliative care or pain control.

Medical and scientific judgement should be exercised in deciding whether expedited reporting is appropriate in other situations such as important medical events that may not be immediately life-threatening or result in death or hospitalization and which are NOT definitively related to the underlying malignancy or disease progression but may jeopardize the patient or may require intervention to prevent one of the events listed above.

AMEND #3: 2014-OCT-01

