# 14.3 Sample Size and Duration of Study

The primary study endpoint is Overall Survival (OS). The study is designed to have a power of 90% and a two-sided alpha of 5% to detect a 23% reduction in the continuous risk of death (HR 0.77, which corresponds to an increase of median survival from 4.6 to 6.0 months). It is estimated that 615 events will be required to detect this reduction which would be observed by randomizing 650 patients over approximately 26 months and following them for additional 12 months.

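### Adverse events may be tested by Fisher's exact test on crude incidence, although each patient's collection period depends on treatment duration and survival

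*Protocol*

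**What the plan says.** Protocol section 14.2 (Safety Analysis) fixes three things.

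- Population: "All patients who have received at least one dose of BBI608/Placebo will be included in the safety analysis".
- Measure: "The incidence of adverse events will be summarized by type of adverse event and severity".
- Test: "A Fisher's exact test will be used to compare adverse events between the two arms if required".

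Neither that section nor 10.1.1, which makes patients evaluable from their first dose, says when the counting period ends.

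The collection schedule is set elsewhere. Section 9.1, footnote 1: "Patients are to be assessed every 4 weeks (28 days) while on study medication and until the first regularly scheduled 4 week assessment" that falls at least 28 days after the drug was stopped. Section 9.2 then continues adverse event evaluation every 8 weeks "thereafter until deterioration to ECOG PS 4 or hospitalization for end of life care". Section 12.2 sets no fixed treatment duration and allows treatment past objective progression.

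Laboratory results are handled separately. Section 11.1 lists among the items not recorded as adverse events "laboratory abnormalities for protocol specified tests (these are derived electronically from actual values supplied". The protocol names no between-arm test for them.

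**The concern.** A patient's period of adverse event observation ends with stopping treatment, decline or death, and these are outcomes the drug is meant to change. Fisher's exact test on the proportion with at least one event gives every patient the same weight, whether followed for two months or twelve. Section 14.3 assumes a survival gain, "which corresponds to an increase of median survival from 4.6 to 6.0 months", so under the plan's own alternative the BBI608 arm has more time in which to record disease-related and background events. A significant difference could then reflect longer life rather than harm. If BBI608 patients stopped or died sooner, the same comparison would understate harm. Safety is a named secondary objective (1.2), and 14.1 lists adverse events among the between-arm comparisons.

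**Working it through.** **Inputs from the protocol.** Median survival 4.6 vs 6.0 months, HR 0.77, two-sided 5%, 90% power, 650 patients or 325 per arm (14.3 and Treatment Schema); 282 randomized at closure, so 282/2 = 141 per arm (14.5).

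**Assumptions.** Exponential survival; adverse events observed until death; the same constant event rate in both arms, so that the drug causes none of the events; placebo incidences of 10, 20 and 40%. The documents give no background rates.

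**The plan's own figures first.** Events = 4 × (1.960 + 1.282)² / (ln 0.77)² ≈ 615, as stated. With 195 events the same formula gives 70% power at HR 0.70 (stated 70%) and 45% at HR 0.77 (stated 43%).

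**Observation time.** The exponential mean is median / ln 2: 4.6/0.693 = 6.64 months and 6.0/0.693 = 8.66 months. The share of the BBI608 mean beyond the placebo mean is 1 − 6.64/8.66 = 23%.

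**Incidence of an unrelated event.** With event rate r and death rate m, the proportion with the event before death is r/(r + m). Setting r to give placebo incidence p, the BBI608 incidence is p / [p + (1 − p) × 4.6/6.0].

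- p = 10%: 0.10/(0.10 + 0.90 × 0.767) = 12.7%
- p = 20%: 0.20/(0.20 + 0.80 × 0.767) = 24.6%
- p = 40%: 0.40/(0.40 + 0.60 × 0.767) = 46.5%

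**Chance of a false flag against BBI608.** Sum the two binomial distributions over all tables with two-sided Fisher p ≤ 0.05 and the higher proportion on BBI608.

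| Placebo vs BBI608 incidence | 325 per arm | 141 per arm | Equal windows |
|---|---|---|---|
| 10 vs 12.7% | 15.5% | 7.6% | about 2% |
| 20 vs 24.6% | 25.9% | 12.1% | about 2% |
| 40 vs 46.5% | 36.6% | 15.9% | about 2% |

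**Closed trial, data cut at 23 May 2014.** Dates from 14.5: activation 15 April 2013, 97 patients by 10 January 2014, 282 by closure; uniform accrual within each period is assumed. Mean observation becomes 2.8 vs 3.1 months. With the event rate re-solved for placebo incidences of 20 and 40% at the cut, BBI608 shows 21.6 and 42.5%. At 141 per arm Fisher rejects in 4.6 and 5.3% of trials in either direction (3.9 and 4.7% against BBI608), compared with about 3.5% in either direction with equal windows.

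**Reversal.** If observation on BBI608 were shorter (assumed ratio about 0.78), a 20% placebo incidence would appear as 16.3% on BBI608, and Fisher would favour BBI608 in about 20% of trials at 325 per arm and 10% at 141.

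**Common 56-day window.** Take events with whole-follow-up placebo incidences of 10, 30 and 50%. Within 56 days they show 2.7 vs 2.7%, 9.8 vs 10.1% and 21.3 vs 21.9%. False flags against BBI608 fall to 1.7–3.2% at 325 per arm. The small remainder comes from deaths inside the window.

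**The case against.** Several objections have force.

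- **The test is conditional, and a SAP may set the window.** Both are true. Incidence over a fixed period is compatible with the wording of 14.2, and a SAP that defines such a period would settle the point. The protocol nevertheless names one measure and one test, with no window, beside a schedule that makes follow-up unequal. The point is that mismatch; the absence of SAP detail is no fault.
- **Laboratory toxicity.** A reader might infer that laboratory abnormalities face the same test and the same false-flag rates. The document does not support this. The Fisher sentence covers adverse events, 11.1 keeps protocol-specified laboratory abnormalities out of that category, and no laboratory test is stated. Any such rate would also need stopping times that the protocol does not give.
- **The closed trial.** A reader might infer that a cut-off at unblinding would not help. It would: on the dates in 14.5 it removes most of the bias. Without a cut, collection also becomes asymmetric. Patients kept on BBI608 stay on the 9.1 schedule (9.1.1), while after discontinuation 9.2.1 asks for ongoing events thought related to BBI608.
- **Early-onset events.** The gastrointestinal events that 8.1.4 calls major may arise early, and the scheduled phone calls fall within the first 6 weeks. Unequal late follow-up affects early events little, so the constant-rate model overstates the bias for them.
- **Direction and weight.** A reader might infer that the drug will always look more toxic. The direction depends on which arm is observed longer. No alpha or decision attaches to this test, and for any single event type modelled at the design effect a false flag is less likely than not.

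**Conclusion.** The point holds for adverse events, as an improvement worth making rather than an error that invalidates the design. At the plan's own survival assumption and 325 per arm, an event BBI608 does not cause would be flagged against it in about 16, 26 or 37% of trials at placebo incidences of 10, 20 or 40%, instead of about 2%. At 141 per arm with follow-up to death the figures are about 8, 12 and 16%. With a 23 May 2014 cut-off they are about 4–5% at placebo incidences of 20 and 40%.

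These sizes rest on exponential survival, a constant event rate, assumed background incidences, and observation up to death (collection actually stops somewhat earlier, at ECOG PS 4 or end-of-life hospitalization). Nothing is claimed about false-flag rates for laboratory abnormalities.

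**What to change.** Amend 14.2, Safety Analysis, as follows.

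1. Keep crude incidence by type and grade as a descriptive table.
2. Base any between-arm adverse event test on a common fixed window, for example first dose to week 8, with data cut at the 23 May 2014 unblinding. Up to week 8 both arms share the same week-4 and week-8 visits and the same phone calls. From 28 March to 23 May is 56 days, so essentially all patients in the ITT-March population can complete the window. Truncation by calendar date in later patients applies equally to both arms.
3. For the whole treatment period plus 30 days, report exposure-adjusted event rates, or cumulative incidence with death as a competing event. Read the cumulative incidence at stated times: at the end of follow-up it equals r/(r + m), which is the crude figure again.
4. Summarise laboratory abnormalities over the same common window.

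The cost is a short amendment and some extra tables from dates already collected. The downside is that late-onset events leave the formal test, but they stay in the exposure-adjusted tables.
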